Protocol

Randomized Clinical Trial of Intraoperative ECMO versus Cardiopulmonary Bypass in Lung Transplantation

Amendment 1. September 27, 2017

TABLE OF CONTENTS

DEFINITIONS, ACRONYMS, AND ABBREVIATIONS.

ABSTRACT.

BACKGROUND AND SIGNIFICANCE

ENDPOINTS.

STUDY DESIGN.

STUDY POPULATION.

DEFINITIONS AND MEASUREMENT OF ENDPOINTS.

CLINICAL CENTERS.

DATA COLLECTION.

DATA MANAGEMENT

ANALYTIC PLAN.

REFERENCES.

DEFINITIONS, ACRONYMS, AND ABBREVIATIONS

CPB Cardiopulmonary bypass

ECMO Extracorporeal membrane oxygenation

PGD Primary Graft Dysfunction

STUDY INVESTIGATOR

PI: [name]

Co-Authors

[name]

[name]

[name]

[name]

[name]

[name]

[name]

[name]

ABSTRACT

Title	Randomized Clinical Trial of Intraoperative ECMO vs. Cardiopulmonary Bypass in Lung Transplantation
Background	Cardiopulmonary bypass (CPB) is the current standard of care for intraoperative cardiorespiratory support during lung transplantation. However, the blood-air interface and the need for full systemic anticoagulation may lead to systemic inflammatory response and coagulopathy. Some reports have suggested that intraoperative support with extracorporeal membrane oxygenation (ECMO) in lieu of CPB may be a better alternative with decreased bleeding, blood requirements and rates of primary graft dysfunction (PGD).
Hypothesis	patients on ECMO will have 
• decreased transfusion requirements,• decreased intubation time,• lesser PGD grade at 72 hours• No increase in major adverse events• Pump duration may be longer.
Study Design	A prospective randomized trial comparing intraoperative support with ECMO and CPB. This will be a superiority trial for efficacy and non-inferiority for safety. The allocation ratio will be 1:1.
Number of Participants	40 in each arm
Study Objectives	Determine if ECMO compared to CPB during lung transplantation has a beneficial effect on

	short term outcomes after lung transplantation.
Interventions	When patient need intraoperative cardiopulmonary support, patient would be randomized to ECMO or CPB
Inclusion Criteria	All patients undergoing lung transplantation. Not all patients randomized will need intraoperative support

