Currently, many centers would use one technique or the other and both are considered current standard of care and best practice. At Cleveland Clinic, we have used both methods. The method of support is currently not discussed with patients as both are considered acceptable.

HYPOTHESIS

Our hypothesis is that patients on ECMO will have a decreased transfusion requirements, decreased intubation time, lesser PGD grade at 72 hours without increase in adverse risk. Pump duration may be longer.

ENDPOINTS

Primary

- 1 Bleeding: total PRBC transfusion requirements at 72hours

Secondary

Superiority

1. Ventilation time (days)
2. Intraoperative PRBC transfusion rates
3. Duration of support
4. Primary graft dysfunction (PGD) grade at 72 hours.
5. Transfusion requirement of FFP, platelets, cryoprecipitate at 72 hours.

Non-inferiority:

1. Composite outcome of: 30-day or discharge date (if earlier than 30 days) mortality, bleeding requiring reoperation, new ECMO, new renal failure requiring dialysis

STUDY DESIGN

Randomized clinical trial with an allocation ratio of 1:1, comparing CBP versus ECMO for intraoperative cardiopulmonary support. Study will have a superiority design for efficacy and a non-inferiority design for safety.

Randomization:

All lung transplant patients will be consented preoperatively. Patients will be randomized at the beginning of the case and the configuration of the cardiopulmonary bypass machine will be set accordingly. Not all patients randomized will require intraoperative cardiopulmonary support.

Circuit design:

separate tubing that connects the venous return line directly to the pump head bypassing the venous reservoir. The venous reservoir is still connected and but clamped.

Incision and cannulation:

The type of incision will be at the discretion of the surgeon but can be sternotomy, thoracotomy or clamshell. If patient has a sternotomy and randomized to ECMO, venous cannula should be placed through a percutaneous femoral venous cannula to avoid the potential of air embolus.

Anticoagulation:

ACT target 200-250. Repeat every 30 min. Bolus 5000U, give supplemental doses as needed.

Conversion to full cardiopulmonary bypass:

Give full dose heparin; release the clamp on the venous reservoir after act is above 480.

Reasons to convert from ECMO to CPB intraoperatively:

- Significant bleeding to allow blood to return back to circuit

- Heart remain too distended to allow mobilization

- Air in the circuit

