- The need to fibrillate or arrest the heart

- Hemodynamic instability from positioning

Other safety mechanisms:

- Consider system for rapid transfusion

- Double lumen intubation: the heart does not decompress and there's ejection requiring the need for ventilation.

- Use an urchin or heartnet for heart positioning if necessary

- Once the patient is decannulated, the blood from the circuit can be re-transfused back into the patient

Transfusion triggers:

Transfusion triggers will be hematocrit of .24 and at the discretion of the staff surgeon, anesthesiologist or intensivist. Coagulopathy will be corrected based on Cleveland clinic post cardiectomy bypass protocol (appendix 2) and at the discretion of surgeon, anesthesiologist or intensivist.

Patients will be extubated at the discretion of the staff surgeon and intensivist.

Patients who are consented but not included in the study and patients who are felt to be better candidates for cpb will be followed in a separate registry

NUMBER OF PARTICIPANTS

40 Patients in each arm

Power calculation (based on 2015 CCF outcomes)

- Safety

 - 30 day mortality: 6.2%

Bleeding requiring reoperation: 10.3%
New ECMO: 1.3%
New renal failure requiring dialysis: 10.3%
Composite outcome 18.6%.

Sample size calculation
Non-inferior margin: 5%
90%: 283, 80%:205, 70%: 155
Non-inferior margin: 10%
90%: 77, 80%:56, 70%: 42

Efficacy

PGD grade at 72 h:

0:	24.4%
1:	47.4%
2:	14.1%
3:	14.1%

RBC transfusion

CPB: 14.7(8.4) vs ECMO 9.3(6.9)
90%: 51, 80%:39, 70%: 30

Ventilation time

CPB: 16.5days (27.3) vs ECMO 8.25 (16.4)
90%: 83, 80%:62, 70%: 49

For literature outcomes, see appendix 1.

STUDY POPULATION

The study population will be all patients undergoing lung transplantation at our institution. These patients will be randomized using the block method and allocated to either the CPB or ECMO group. Not all patients randomized will require intraoperative support.

Inclusion Criteria

All consented patients undergoing lung transplantation.

Exclusion Criteria

Patients undergoing concomitant cardiac operations with indication for obligate use of cardiopulmonary bypass

Patient with specific anatomy that require full cardiac decompression such as severe pulmonary hypertension or large heart that are shifted severely into the left chest (relative)

Patients with high likelihood of significant pleural bleeding that will require returning the blood back into the cardiotomy reservoir (relative)

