Patients bridged to transplant with ECMO

Cystic fibrosis/bronchiectasis/resistant infection patients where surgeon will need to remove both lungs prior to implantation

Patients who the surgeon feels would be better served with CPB rather than ECMO
These patients will be entered into a registry and followed.

CLINICAL CENTERS

Patient Confidentiality

All patient records will be kept confidential according to HIPAA guidelines. Study investigators and site Institutional Review Boards (IRBs) may review source documentation as necessary, but will then transmit this information to Clinical Investigations at Cleveland Clinic according to the patient's unique study number. Linkage of that study number to the actual patient will reside only at the individual institutions. Aggregate data from this study may be published as per publication policy documented in the trial agreements; no data with patient identifiers will be published.

Consent

Patients will be consented for surgery ahead of time at time of listing

DATA COLLECTION

Data will be collected from Epic Systems chart review and supplemental data collection. All necessary data are currently already collected. Study terminates at patient discharge. No additional testing or followup is needed beyond what is already done for this patient population.

DATA MANAGEMENT

The data will be stored in Red Cap Sheets strictly secured and managed by the lead and other co-investigators. No identifiable information will be shared with outside parties, ensuring that all data will remain safely stored on Cleveland Clinic Main Campus user hard drives and will only be shared amongst our study team.

ANALYTIC PLAN

Basic statistical analysis will be required to compare the outcomes in the groups. Patients who are excluded will be included in a separate registry.

Analysis will be based on intention to treat.

A statistical significant difference is defined as a two-sided P value less than 0.05.

REFERENCES

1. Machuca (2015) Outcomes of intraoperative extracorporeal membrane oxygenation versus cardiopulmonary bypass for lung transplantation.
2. Bermudez (2014) Outcomes of Intraoperative Venoarterial Extracorporeal Membrane Oxygenation Versus Cardiopulmonary Bypass During Lung Transplantation.
3. Ius (2012) Lung transplantation on cardiopulmonary support: Venoarterial extracorporeal membrane oxygenation outperformed cardiopulmonary bypass.

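### Support is started after an open allocation and without a stated criterion, so patients actually supported in the two arms cannot be assumed comparable; expected support should be recorded before allocation.

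*Combined protocol and SAP*

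**What the plan says.** Under Study Design, Randomization: "Patients will be randomized at the beginning of the case and the configuration of the cardiopulmonary bypass machine will be set accordingly". The next sentence adds: "Not all patients randomized will require intraoperative cardiopulmonary support". The Inclusion row of the Abstract and the Study Population section say the same in substance. The Interventions row of the Abstract gives a different timing: "When patient need intraoperative cardiopulmonary support, patient would be randomized to ECMO or CPB".

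The protocol lists reasons for converting from ECMO to CPB but gives no criterion for starting support in either arm. No masking is described, and cannulation depends on the arm: "If patient has a sternotomy and randomized to ECMO, venous cannula should be placed through a percutaneous femoral venous cannula". The operating team must therefore know the allocation.

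The Hypothesis section is worded by device received: "Our hypothesis is that patients on ECMO will have a decreased transfusion requirements". Duration of support is a secondary superiority endpoint. The Analytic Plan says "Analysis will be based on intention to treat" and does not say how patients who received no support enter the analysis or the duration endpoint.

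**The concern.** Need for support is judged after the allocation is known, and the team knows which circuit stands ready. The protocol itself attributes different burdens to the two circuits: full heparinisation and its bleeding risk for CPB, a lower ACT target under Anticoagulation, and femoral venous cannulation for ECMO after sternotomy. A marginal patient could be put on support in one arm and finished without it in the other. The supported groups would then differ in case mix as well as in device.

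This is distinct from the loss of power caused by unsupported patients, which arises even when both arms use support equally. Here the set of supported patients itself may depend on the arm. At stake are the duration endpoint, any PRBC comparison restricted to supported patients, and the interpretation of the intention-to-treat result as an effect of the circuit alone.

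**Working it through.** **1. The plan's own figure.** Number of Participants gives mean RBC use of 14.7 (SD 8.4) for CPB and 9.3 (SD 6.9) for ECMO, a difference of 5.4 units, with 51 / 39 / 30 per arm for 90 / 80 / 70% power. With n = 2(1.96 + z)² × 8.4² / 5.4², the result is 51 / 38 / 30; the t-test version gives 51.8 / 39.0 / 30.9. The figures reproduce with the CPB SD in both arms. The 5.4 units serve as the yardstick below.

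**2. Supported patients only, no true device effect.** None of these inputs except 14.7 is in the documents:
- a share pA of patients is supported in either arm, using 14.7 units on either device;
- a further share pB is supported only if the circuit is ECMO, using m units on it.

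Apparent ECMO advantage = 14.7 − (14.7 pA + m pB)/(pA + pB) = (14.7 − m) × pB/(pA + pB).

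| pA | m | pB = 0.05 | pB = 0.20 |
|---|---|---|---|
| 0.60 | 7 | 7.7 × 0.05/0.65 = 0.59 | 7.7 × 0.20/0.80 = 1.93 |
| 0.50 | 7 | 7.7 × 0.05/0.55 = 0.70 | 7.7 × 0.20/0.70 = 2.20 |
| 0.70 | 7 | 7.7 × 0.05/0.75 = 0.51 | 7.7 × 0.20/0.90 = 1.71 |
| 0.60 | 12 | 2.7 × 0.05/0.65 = 0.21 | 2.7 × 0.20/0.80 = 0.68 |

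The span is about 0.2 to 2.2 units, or 4% to 41% of 5.4. The value of m matters most. If the marginal patients are instead supported only on CPB, the same formula gives the same sizes against ECMO. If pB = 0, the artefact is zero.

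**3. Cross-check with another model.** Let need for support be standard normal, with the neediest share s supported, and let PRBC use (SD 8.4) correlate r with need. Mean need among the supported is φ(t)/s, with t = Φ⁻¹(1 − s). The apparent ECMO advantage is 8.4 × r × [φ(t₁)/s₁ − φ(t₂)/s₂], where 1 is CPB and 2 is ECMO. For r = 0.3 / 0.5 / 0.7:
- 60% vs 60% supported: 0 units, type I error 5%.
- 60% vs 80%: 0.7 / 1.2 / 1.7 units, type I error 6 / 9 / 14%.
- 50% vs 80%: 1.1 / 1.9 / 2.6 units, type I error 8 / 14 / 25%.

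The order of magnitude is the same. The shares and r are again assumptions.

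**4. All randomised patients.** Under the model in step 2, the CPB minus ECMO difference is pB × (units without support − units on ECMO). With 5 and 7 units this is −0.1 at pB = 0.05 and −0.4 at pB = 0.20, that is, 2% to 7% of 5.4 and against ECMO. It scales with the assumed gap of 2 units. If support added 3 units and use differed by 10 points, it would be −0.3; with 8 units and 30 points, −2.4. This is a real consequence of the assigned strategy, not a selection bias, but it is not a difference between circuits.

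**The case against.** The strongest reply is that the plan names only an intention-to-treat analysis. No on-support analysis of PRBC appears anywhere, and the hypothesis wording may be loose language for the assigned arm. This stands. The larger figures in steps 2 and 3 apply to an analysis the plan does not name.

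A reader might infer that the primary result is biased, or biased towards ECMO. The documents support neither. The all-randomised comparison is protected by randomisation. The direction of any selection is open: femoral cannulation could discourage ECMO in marginal cases, and the Abstract calls CPB the current standard. A reader might also infer that the supported groups are known to differ. They cannot be assumed comparable, but equal use with the same selection would leave no bias. That the surgeon alone makes the decision is likewise an inference; the argument needs only an unmasked operating team.

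Two further points stand. Duration could be set to zero for unsupported patients, so it is not strictly confined to supported ones; the plan does not say. And if the timing in the Interventions row applied, the problem would largely disappear. That row conflicts with the Study Design and Study Population sections and with the Abstract's own Inclusion row, so the conflict needs reconciling and does not answer the point.

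**Conclusion.** The point holds in a limited form. On the Study Design text, support is decided after an open allocation and without a criterion, so patients supported in the two arms cannot be assumed comparable. Intention to treat remains a valid comparison of strategies; the illustrative shift is 0.1 to 0.4 units, resting on an assumed 2-unit cost of support and larger if that cost is larger. Duration of support among supported patients, and any comparison by device received, are exposed to post-randomisation selection of about 0.2 to 2.2 units of PRBC for the latter, in either direction. The support shares, marginal PRBC values and correlations are all assumptions. This is an inexpensive improvement to the plan, not a flaw that invalidates the primary analysis.

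**What to change.** 1. Reconcile the time of randomisation between the Interventions row of the Abstract and the Study Design and Study Population sections.
2. If randomisation stays at the start of the case, record expected support (planned / possible / not expected, with the indication) before allocation is opened. A judgement free of the allocation cannot be recovered later from the chart.
3. Keep intention to treat as primary, state that all randomised patients count whether supported or not, and include this entry as a baseline covariate. It adds precision to the extent that it predicts PRBC use.
4. Define any supported-patient analysis by this entry, never by support given.
5. Report support use, with reason, by arm.
6. State in advance that duration of support among supported patients is descriptive. This should not depend on whether the observed proportions differ: at 40 per arm they may differ by chance, and equal proportions do not ensure equal case mix.

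The cost is one form field and a few sentences in the Analytic Plan, with no extra patients or procedures. The downside is small: the entry predicts actual support imperfectly, so a subset defined by it will still contain some unsupported patients.

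### One abstract row contradicts start-of-operation randomisation, and the sample size states no allowance for randomised patients who receive neither device

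*Combined protocol and SAP*

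**What the plan says.** **Time of randomisation.** The abstract's Interventions row reads: "When patient need intraoperative cardiopulmonary support, patient would be randomized to ECMO or CPB". The Randomization paragraph under Study Design reads: "Patients will be randomized at the beginning of the case and the configuration of the cardiopulmonary bypass machine will be set accordingly".

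**Unsupported patients.** The plan says three times that some randomised patients will not go on a device: in the abstract's Inclusion Criteria row ("Not all patients randomized will need intraoperative support"), under Study Design ("Not all patients randomized will require intraoperative cardiopulmonary support") and under Study Population ("Not all patients randomized will require intraoperative support"). No expected proportion is given.

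**Size.** Number of Participants gives "40 Patients in each arm". For red-cell transfusion it lists a mean (SD, as I read it) of 14.7 (8.4) for CPB and 9.3 (6.9) for ECMO, with 51, 39 and 30 per arm for 90, 80 and 70% power. It does not say which power is adopted; 40 is one more than the 80% figure.

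**Analysis.** The Analytic Plan specifies intention to treat, with significance at a two-sided P below 0.05. No other analysis set is named.

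**The concern.** Randomising at need and randomising at the start of the operation give different trial populations. In the first, every randomised patient is expected to go on a device, and the primary comparison is of the devices in supported patients. In the second, the comparison is of allocation to the devices among all enrolled transplant patients. The second is a legitimate question, but its expected difference is smaller, because patients who receive neither device contribute no contrast between devices.

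The red-cell means are labelled CPB and ECMO, so they appear to describe patients who were on those devices. If they do, the planned difference of 5.4 units belongs to the first population and the analysis to the second. A real device effect on the primary endpoint would then be easier to miss than the stated calculation suggests.

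**Working it through.** **1. Which randomisation time is operative.** If patients were randomised only once support was needed, the three statements that some randomised patients will not need it could not hold. They fit only start-of-operation allocation, as does the Randomization paragraph, which ties allocation to how the machine is set up. That is four statements against one abstract row, and the same abstract's Inclusion Criteria row contradicts it.

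**2. The plan's own figure.** Inputs: difference 14.7 − 9.3 = 5.4; two-sided alpha 0.05; 1:1 allocation. Smallest n per arm for 90/80/70% power (plan: 51/39/30):

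| Inputs | Method | n per arm |
|---|---|---|
| SD 8.4 in both arms, f = 0 | normal approximation, 2 × (8.4 × (z_α/2 + z_power) / 5.4)² | 51 / 38 / 30 |
| SD 8.4 in both arms, f = 0 | noncentral t | 52 / 39 / 31 |
| SDs 8.4 and 6.9, f = 0 | noncentral t (Welch) | 44 / 33 / 27 |
| SDs 8.4 and 6.9, f = 8% | noncentral t (Welch) | 52 / 39 / 31 |

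The larger SD in both arms with no allowance reproduces the plan to within one patient. So does an allowance of about 8% with the two stated SDs. How 39 was derived therefore cannot be settled; what can be said is that no allowance is stated.

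**3. Dilution.** Let f be the unsupported fraction in each arm. Suppose that need for support, and transfusion in unsupported patients, do not depend on arm. Then the intention-to-treat difference is 5.4 × (1 − f).

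**4. Power at 40 per arm.** The noncentrality parameter is 5.4 × (1 − f) / SE.

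- SDs 8.4 and 6.9: SE = √((70.56 + 47.61)/40) = 1.719; at f = 0, 5.4/1.719 = 3.14.
- SD 8.4 in both arms: SE = √(141.12/40) = 1.878; at f = 0, 5.4/1.878 = 2.875.

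| f (assumed) | Difference | Power, SDs 8.4 and 6.9 | Power, SD 8.4 in both arms |
|---|---|---|---|
| 0 | 5.40 | 87% | 81% |
| 5% | 5.13 | 84% | 77% |
| 10% | 4.86 | 80% | 72% |
| 20% | 4.32 | 70% | 62% |
| 30% | 3.78 | 58% | 51% |

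Power reaches 80% at f = 9.7% with the stated SDs and at f = 1.3% with SD 8.4 in both arms.

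**5. Is this an artefact of a constant SD?** Give unsupported patients an assumed mean of 2 units and SD of 2, so that each arm's variance is (1 − f)·SD² + f·2² + f(1 − f)(mean − 2)². Power becomes 77%/71%, 66%/60% and 54%/50% at f = 10, 20 and 30%. That is about 1 to 4 points lower than in the table, so the loss does not come from the simplification.

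**6. Supported patients only.** The difference is the full 5.4 units, in fewer patients. At f = 20%, 40 × 0.8 = 32 per arm gives 79%/72%.

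**The case against.** **The text already answers the main question.** One abstract row is out of line, and the body is consistent. Study Population says "These patients will be randomized using the block method and allocated to either the CPB or ECMO group"; with block randomisation and intention to treat, an arm naturally means the patients randomised to it. This stands. A reader might infer that the target of the primary test cannot be determined, but that is too strong. What remains is a contradictory row to correct and a count to define in a phrase.

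**Any single power figure rests on an invented f.** This also stands. Nothing in the documents points to 20%. A reader might infer that the trial has only 62–70% power; the documents do not support that. With the stated SDs there is no material shortfall from 80% until f exceeds about 10%.

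**The dilution formula assumes need is independent of arm.** It does, and the machine is configured to the arm beforehand, so need may be judged with the arm known. With an average f of 20%, unsupported patients averaging an assumed 2 to 6 units and the SDs held constant, 15% unsupported in the ECMO arm and 25% in the CPB arm gives roughly 42–57% power; the reverse gives roughly 74–86%. Conversions from ECMO to CPB, which intention to treat counts as ECMO, are also left out. The table shows how power responds to f; it does not predict the trial's power.

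**Randomised, unsupported patients might be thought to move to the registry.** The registry takes "Patients who are consented but not included in the study". A randomised patient under intention to treat is not in that category, and no passage says that such patients leave the trial.

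**Conclusion.** The point holds in limited form. Two things are certain from the text: the Interventions row contradicts the operative start-of-operation randomisation, and the red-cell calculation states no allowance for unsupported patients although the plan expects some.

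The size of the consequence is conditional. Across f from 0 to 30%, power at 40 per arm runs from 87% down to 58% with the stated SDs, and from 81% down to 51% with SD 8.4 in both arms. The first case has room up to f of about 10%; the second has almost none. These figures assume that the device-labelled means describe supported patients, that need is independent of arm, and that conversions are ignored.

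A reader might go further and conclude that the sample size was derived without any allowance. The documents do not show this, since 39 per arm arises either way. Nor is the all-randomised comparison a mistake: it is a valid question whose power has not been stated.

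**What to change.** 1. Reconcile the Interventions row with the Inclusion Criteria row, Study Design and Study Population on the time of randomisation. State that the 40 per arm counts randomised patients or, if supported patients are meant, say so.
2. If start-of-operation allocation stays, keep all-randomised intention to treat as the primary analysis. Take f from institutional records and restate power at 40 per arm over a plausible range of f. No patients need be added.
3. Add a sensitivity analysis in supported patients for the primary endpoint and the safety composite. It should not be the primary set, because need may be judged with the arm known and the supported groups may then not be comparable.

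As a side clarification, state whether unsupported patients enter the duration-of-support endpoint as zero, as missing or not at all.

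The cost is protocol wording, one planning figure from existing records and one extra analysis of data already collected. The downside is a less favourable stated power and slightly more analysis.

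### The incision may be chosen after the allocation is known, so it may differ by arm and weaken attribution of a PRBC or ventilation difference to the support method alone

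*Combined protocol and SAP*

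**What the plan says.** Study Design, Randomization: "Patients will be randomized at the beginning of the case and the configuration of the cardiopulmonary bypass machine will be set accordingly". The order of randomisation and incision is not stated.

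Study Design, Incision and cannulation: "The type of incision will be at the discretion of the surgeon but can be sternotomy, thoracotomy or clamshell". The next sentence reads: "If patient has a sternotomy and randomized to ECMO, venous cannula should be placed through a percutaneous femoral venous cannula", and gives avoidance of air embolus as the reason. No corresponding statement is made for CPB.

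The Interventions row of the Abstract gives a different time for randomisation: "When patient need intraoperative cardiopulmonary support, patient would be randomized to ECMO or CPB".

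Study Population: "These patients will be randomized using the block method and allocated to either the CPB or ECMO group". No stratification factor is named. The Analytic Plan describes a basic comparison of the groups by intention to treat, with two-sided P below 0.05. It names no covariates and does not mention incision. The primary endpoint is "Bleeding: total PRBC transfusion requirements at 72hours"; ventilation time is a secondary superiority endpoint. No blinding of the operating team is described.

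**The concern.** Under the Study Design text, the circuit is set up by arm at the start of the case, so the surgeon can know the arm when choosing the incision. The sternotomy rule then makes one consequence of that choice depend on the arm. This could give an arm-specific reason to prefer one incision over another.

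If the incision mix did differ by arm, and if incision affects blood loss or time to extubation in its own right, the observed difference would combine the circuit with the incisions that came with it. The stated objective is the effect of ECMO compared with CPB. A reader would want to know how much of any difference belongs to the circuit, and the plan collects nothing before allocation that would help answer this. Adjusting afterwards for the incision actually made is not a remedy: that choice follows allocation, and conditioning on it can itself introduce bias.

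**Working it through.** **1. Timing, side by side.** Under the Study Design text, the allocation may be known before the incision. Under the Abstract text, randomisation waits for the need for support, which would usually come after the incision; the mechanism then largely disappears. The Abstract, Study Design and Study Population all say that not every randomised patient will need support, which fits early randomisation better. The documents do not settle the matter.

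**2. The plan's own sample size.** Inputs from Number of Participants: RBC transfusion 14.7 (SD 8.4) on CPB and 9.3 (SD 6.9) on ECMO; stated n per arm 51, 39 and 30 for 90%, 80% and 70% power; 40 per arm planned.

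- Difference: 14.7 − 9.3 = 5.4 units.
- Normal formula: n = 2 × SD² × (1.960 + z)² / 5.4². With SD 8.4 and 80% power: 2 × 70.56 × (1.960 + 0.842)² / 29.16 = 38.0.
- All three power levels: 51, 38 and 30 by the normal formula; 52, 39 and 31 by the t-test. The stated figures are reproduced to within one patient.
- The pooled SD, √((8.4² + 6.9²)/2) = 7.69, gives 43, 32 and 26, which match only after an inflation for a rank test. The document does not say which route was used.
- Power at 40 per arm for 5.4 units (t-test): 81% with SD 8.4, 87% with SD 7.69.

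**3. Illustrative size.** The documents give no incision mix and no incision effect, so both factors below are assumptions.

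Shift in arm difference = (between-arm difference in incision share) × (PRBC difference between incisions).

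The last two columns use a two-sided 0.05 t-test, SD 8.4 and 40 per arm. Power is for a true circuit effect of 5.4 units with the shift working against ECMO. The rejection rate is for no true circuit effect.

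| Assumed share difference × units | Shift | Share of 5.4 | Power | Rejection rate |
|---|---|---|---|---|
| none | 0 | 0% | 81% | 5.0% |
| 10 points × 1 | 0.1 | 2% | 80% | 5.0% |
| 20 points × 2 | 0.4 | 7% | 75% | 5.5% |
| 30 points × 3 | 0.9 | 17% | 66% | 7.6% |
| 40 points × 4 | 1.6 | 30% | 52% | 13.4% |

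The shift could equally favour ECMO; the documents give no basis for a direction. A 40-point move away from sternotomy on ECMO also requires at least 40% sternotomy in the CPB arm, which is unknown. Modest imbalances matter little; only a large imbalance combined with a large incision effect matters much.

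No such calculation is possible for ventilation time without assuming an incision effect in days, for which the documents give no starting point.

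**The case against.** Four points can be made against this, and most of them stand in part.

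- **Knowledge of the arm is an inference.** A reader might infer that the surgeon always knows the allocation before cutting. The documents do not say so: Study Design gives no order, and the Abstract's timing would usually reverse it. The supported statement is that the allocation may be known.
- **The cannulation rule is not shown to be a burden.** A reader might infer that ECMO patients with a sternotomy get an extra femoral cannulation that CPB patients are spared. The text says only where the ECMO venous cannula goes. CPB cannulation is not described, so the contrast rests on silence. The rule can equally be read as making sternotomy workable on ECMO, and that surgeons would avoid sternotomy is conjecture. It also has no evident practical force for patients who are never cannulated.
- **This is not confounding.** A reader might infer that the primary comparison is invalid. It is not. An incision chosen because of the allocation is a consequence of the assignment, and intention to treat still compares the two strategies validly, including the incision choices they bring about. Only attribution to the circuit alone is weakened.
- **Covariates do not undo a shift.** Adjusting for planned incision balances a baseline factor and may add precision. It does not remove a change of incision made after allocation. This is correct, and it is why the by-arm table is needed as well.

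What remains is that the incision is discretionary, may follow allocation, and is neither recorded as a plan beforehand nor set to be reported by arm.

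**Conclusion.** The point holds as a limit on interpretation. As Study Design is written, incision type may differ by arm as a post-randomisation co-intervention, and the plan offers no means of seeing this or of judging how far a PRBC or ventilation difference belongs to the support method.

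The size cannot be determined from the documents. The range of 0.4 to 1.6 PRBC units rests wholly on assumed shifts of 20 to 40 points and assumed differences of 2 to 4 units. It falls towards zero under weaker assumptions, and largely goes away if randomisation takes place only when support is needed. The low end is minor. The high end would not be, since 40 per arm leaves almost no reserve over the 39 stated for 80% power. The change is worth making because it costs almost nothing and because a pre-allocation plan cannot be recovered without bias later.

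**What to change.** 1. Reconcile the Abstract and Study Design on when randomisation happens, and state its order relative to the incision.
2. Before the allocation is opened, have the surgeon record the planned incision (sternotomy, thoracotomy or clamshell) and single or double lung.
3. Name these planned factors as pre-specified covariates in the PRBC and ventilation analyses, or stratify the blocks on them. Do not adjust for the incision actually made.
4. Report actual incision, cannulation and departures from plan by arm.

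The choice of incision stays with the surgeon; no rule that the plan must be followed is proposed.

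The cost is one extra line on the randomisation form and one or two covariates. If stratification is chosen, the strata should be few, given 40 per arm. The limit of the remedy should be stated openly: adjustment improves precision but does not remove a post-allocation shift, which the by-arm table only makes visible.
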